2.1 Objective and hypothesis

The objective of the SafeBoosC III follow-up study is to investigate the benefits and harms of treatment guided by cerebral NIRS monitoring of brain oxygenation in extremely preterm infants during the first 72 hours of life, assessed at two years' corrected age.

The hypothesis is that the intervention will decrease a composite of death or moderate-or-severe neurodevelopmental disability at two years' corrected age, and/or increase cognitive function in survivors assessed by the Bayley III/IV test, with insignificant harms.

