2.5 Outcomes

2.4.1 Primary outcomes

The two co-primary outcomes are:

1) Death or moderate-or-severe neurodevelopmental disability (NDD).

A child will be classified with moderate-or-severe NDD if any of the four following conditions are present:

- cerebral palsy with functional impairment corresponding to Gross Motor Function Classification Score (GMFCS) ≥ 2 ;
- a score below -2 standard deviations from the norm of a standardised developmental assessment (if using the Bayley III/IV test, the cognitive score cut-off will be < 85), or an informal classification of moderate-or-severe NDD;
- vision impairment defined as moderately reduced vision, or only being able to perceive light or light reflecting objects; or blind in one eye with good vision in the contralateral eye.
- hearing impairment defined as hearing loss corrected with aids (usually moderate 40-70dBHL) or some hearing loss not corrected by aids (usually severe 70-90dBHL).

2) Bayley III/IV mean cognitive score

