2.12 Data management plan

All the participating children's data are protected in accordance with the Danish Act on the processing of personal data and the Danish Health Act. Data entry will be managed through a web-based clinical trial software, OpenClinica, provided by Copenhagen Trial Unit. The electronic case report form has already been used as the platform for data entries in the SafeBoosC-III trial, using end-to-end encryption. For this follow-up study, an additional data entry module will be added to the SafeBoosC-III OpenClinica setup. Data will be stored in accordance with guidelines issued by the Danish Data Protection Agency, where the follow-up study will also seek approval from. Data are pseudonymised, only NICU numbers and study numbers are used to identify children. Personal identifying information linking to study numbers will be kept in the trial master file at the local NICU.

Six months after the acceptance of the main publication presenting the primary outcome, the dataset will be transferred to the Danish data archive, after re-coding of variables (birth weight, gestational age, sex, NICU, study number) that may be used for reidentification. This data set can be made available for others as decided by the trial steering committee. Due to the residual risk of re-identification, the dataset will not be placed in public space.

3 Statistical analysis plan

Full details regarding statistical considerations and data analysis will be outlined in a separate report, which will be published before the analysis of the SafeBoosC-III trial data, expected late spring 2022.

Power estimations for the co-primary outcomes

The sample size of 1600 infants for the SafeBoosC-III trial is based on mortality and the prevalence of survivors with severe brain injury in the SafeBoosC II trial, i.e. a 22% relative risk reduction in the composite primary outcome from 34% to 26.5% (absolute risk reduction of 7.5%), at an alpha level of 5%, and a power of 90%. The latest Data Monitoring Report from March 2021 revealed a tentative mortality rate of 21% in the SafeBoosC-III trial, based on first 580 randomised infants. Assuming the mortality rate will stay constant, there will be 1264 infants alive at two years of corrected age, and thus, be available for follow-up assessment.

Death or moderate-or-severe neurodevelopmental disability power calculation

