Based on answers from the questionnaire on systematic routine follow-up, as well as implementing parental questionnaires and informal assessments to classify neurodevelopment, we estimate the total sample size for the outcome death or moderate-or-severe NDD to 1600 children.

Based on results from two randomised controlled clinical trials (49,50) investigating neuroprotection in preterm infants, it is estimated that the proportion of children with the outcome death or moderate-or-severe NDD will be 50% in the control group. An indicative power calculation shows that if we want to test an absolute risk difference of eight percentage, between the experimental and control group, at an alfa of 2.5% and a sample size of 800 infants in each group, i.e. a total of 1600, we will reach a power of 80%.

Bayley III/IV mean cognitive score power calculation

Based on answers to a questionnaire on systematic routine follow-up from participating NICUs in the SafeBoosC-III consortium (see section 1.5 ‘recruitment and loss to follow up), it is expected that 65% of the NICUs will be able to provide data from a Bayley III/IV assessment around two years of corrected age for each child. Assuming that these NICUs enrol their proportion of the 1600 infants to the SafeBoosC-III trial, and a mortality rate of 21% (12), approximately 850 infants will be available for Bayley III/IV assessments at two years of age.

An indicative power estimation shows, that if we want to test a mean difference of five points on the Bayley cognitive score, with a standard deviation of 20 (Cohens d' 0.25) between the experimental and the control group, at a 2.5% alfa-level, with a sample size of 425 infants from each group in the follow-up study i.e. a total of 850, we will reach a power of 90%.

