3.1 Primary analyses

The primary analysis of all outcomes will be based on the intention-to-treat population. Mixed-effect linear regression and mixed-effect logistic regression will be used to analyse the dichotomous and continuous co-primary outcomes, respectively. Data from all participating sites will be used in the primary analysis of both co-primary outcomes. In the regression models, 'site' will be included as a random effect, while 'gestational age below or above 26 weeks of postmenstrual age' and 'group allocation' will be included as fixed effects. To correct for multiple testing, the threshold for statistical significance will undergo Bonferroni adjustment, and thus a p-value of 0.025 for each primary outcome is chosen. Superiority of the intervention will only be claimed if at least one of the two co-primary outcomes is statistically significant. All other outcome results will be considered hypothesis-generating only. In addition, we will perform a range of pre-defined sensitivity analyses to inform the interpretation of the results of the primary analysis. A full statistical analysis plan will be developed and submitted for publication before the analysis of the SafeBoosC-III trial data.

[figure not shown]

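### Optional improvement, not an error: a direction-gated step-down rule would keep the 5% familywise bound and the same superiority decision as Bonferroni, with more power for the second co-primary outcome

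*Combined protocol and SAP*

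**What the plan says.** Section 3.1 sets the multiplicity rule: "the threshold for statistical significance will undergo Bonferroni adjustment, and thus a p-value of 0.025 for each primary outcome is chosen". The decision rule follows: "Superiority of the intervention will only be claimed if at least one of the two co-primary outcomes is statistically significant". Neither sentence contains a step-down element, so each outcome is judged at 0.025 whatever the other shows.

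The power calculations in section 3 use the same level. For death/NDD the wording is "at an alfa of 2.5% and a sample size of 800 infants in each group", and for Bayley it is "at a 2.5% alfa-level, with a sample size of 425 infants from each group". The summary agrees.

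Section 2.1 gives both outcomes a direction: the composite should fall, "and/or increase cognitive function in survivors assessed by the Bayley III/IV test, with insignificant harms". The composite counts deaths, while Bayley is measured only in survivors.

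Two things are not written down. The 5% family level follows from 2 x 0.025 but is not stated for these outcomes, and no section says whether the tests are two-sided. Section 3 also defers detail: "Full details regarding statistical considerations and data analysis will be outlined in a separate report".

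**The concern.** Bonferroni is the simplest rule that bounds the familywise error of two tests, but it is not the most powerful. Holm compares the smaller p-value with 0.025 and, if that is significant, the other with 0.05. It keeps the same 5% bound under any dependence and rejects everything that Bonferroni rejects.

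What is at stake is the conclusion on the second co-primary outcome. Suppose Bayley favours the intervention with p below 0.025 and death/NDD gives p = 0.03. Under section 3.1 the death/NDD result must be reported as not significant, although a valid 5% procedure would allow the claim. The two outcomes answer different questions (death or disability in all infants, cognition in tested survivors), so the second conclusion has value of its own.

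**Working it through.** **Inputs.** From section 3: death/NDD 50% v 42%, 800 per group; Bayley difference 5 points, SD 20, 425 per group; 0.025 per outcome. Assumed: two-sided tests, and a correlation between the two test statistics (benefit counted as positive) of 0.2 to 0.5.

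**1. The plan's own figures.** 0.025 + 0.025 = 0.05. The two-sided 0.025 critical value is 2.241; the 0.05 value is 1.960.
- Death/NDD: SE = sqrt((0.50 x 0.50 + 0.42 x 0.58)/800) = 0.0248; expected z = 0.08/0.0248 = 3.22; power 83.6% (83.4% with a pooled variance). The plan states 80%, which holds as a floor.
- Bayley: SE = 20 x sqrt(4/850) = 1.372; expected z = 5/1.372 = 3.64; power 92.0%. The plan states 90%.

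**2. The alternative rule.** Compare the smaller p-value with 0.025. If it is significant in favour of the intervention, compare the other with 0.05; otherwise compare the other with 0.025.
- Everything this rule rejects, Holm also rejects, so familywise error stays at or below 5% under any dependence.
- Everything Bonferroni rejects, this rule also rejects.
- The 0.05 level is reached only when the other outcome is already favourable at 0.025. Superiority has then already been claimed, so that decision cannot change.

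**3. Smallest significant observed difference for the second outcome.**
- Death/NDD: 2.48 x 2.241 = 5.6 percentage points falls to 2.48 x 1.960 = 4.9.
- Bayley: 1.372 x 2.241 = 3.1 points falls to 1.372 x 1.960 = 2.7.

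**4. Operating characteristics** (bivariate normal; ranges are for correlation 0.2, then 0.5).

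| Truth | Quantity | Bonferroni | Step-down rule |
|---|---|---|---|
| Both planned effects | death/NDD significant | 83.6% | about 89% |
| | Bayley significant | 92.0% | 94.5-94.0% |
| | both significant | 77.7-79.4% | 85.6-86.5% |
| | at least one | 97.8-96.2% | same |
| Both effects halved (50% v 46%; 2.5 points) | both significant | 11.3-15.4% | 17.9-22.6% |
| Bayley as planned, death/NDD halved | death/NDD significant | 26% | 35-36% |
| One effect real, the other null | null outcome declared significant | 2.5% | about 4.3-4.8% |
| Both null | any false rejection | 4.9-4.6% | same |

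If only one effect is real, the power for that outcome rises by 0.03 points or less. In simulation of the rule the superiority decision differed from Bonferroni's in no draw.

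**5. Why the direction condition.** Suppose death/NDD is truly 8 points worse (50% v 58%) and survivors' Bayley truly 2.5 points better. The chance of a favourable Bayley claim is 33.8% under Bonferroni, 42.7% under ordinary Holm and 33.8% under the proposed rule. The condition does not hide the harm: the death/NDD difference is detected in 83.6% of trials under Bonferroni and in 86-87% under the proposed rule.

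**6. What the plan says about the correlation.** Section 3 reports a "tentative mortality rate of 21% in the SafeBoosC-III trial" and assumes 50% for the control composite, so NDD in survivors is (0.50 - 0.21)/0.79 = 36.7%. Section 2.4.1 sets the threshold: "if using the Bayley III/IV test, the cognitive score cut-off will be < 85". If scores are normal and all NDD is Bayley below 85, the correlation is 20 x 0.377 x sqrt(425/800)/(20 x 0.5) = 0.55. At 0.55 the power for both goes from 79.8% to 86.7%. Lower values need further assumptions: if 10% or 20% of survivors score below 85 and the other components are independent of the score, the correlation is 0.18 or 0.32.

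**The case against.** **Nothing is broken.** The present rule is valid, simple and used consistently. Superiority needs only one outcome, and at least one succeeds in 96-98% of trials under either rule at the planned effects. This stands, and it is why the point is optional. A reader might infer that Bonferroni is a mistake here, that the trial is underpowered because of it, or that changing it raises the chance of claiming superiority. The documents support none of these: the power figures are met at 0.025, and the superiority decision is the same under both rules.

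**Blinding.** Sections 2.8 and 3.2 keep the statisticians and those drawing conclusions blinded. Bonferroni can be applied to coded groups. A threshold that depends on which group is favoured cannot, unless results are reported under both codings. This stands, and the fix provides for it.

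**Benefit and harm are treated differently.** If both outcomes are truly harmed at the planned size, both are declared significant in 77.8-79.4% of trials, as under Bonferroni, against 85.7-86.5% under ordinary Holm. The whole gain in declaring both outcomes goes to benefit, although harms are part of the stated objective. Nothing becomes worse than in the current plan, but the asymmetry must be disclosed.

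**Intervals and error.** A 97.5% interval for the second outcome can include the null while the outcome is called significant, and the error on a null second outcome rises within the 5% limit. A sponsor who values matching intervals more can reasonably keep Bonferroni.

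**Best-case sizes.** Section 1.5 does not expect all eligible children to take part, and Appendices A and B allow unclassifiable children. The absolute powers are therefore upper figures.

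**The separate plan** could still add a step-down rule, but section 3.1 already fixes Bonferroni, so a change made only there would contradict it.

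**Conclusion.** A worthwhile, low-cost improvement to a valid plan. The familywise bound and the unchanged superiority decision follow from logic and need no assumption about correlation. The size of the gain does: with both planned effects real and correlation 0.2-0.5, it is about 5 points for death/NDD, 2 to 2.5 for Bayley and 7 to 8 for both together. It requires that both outcomes are truly affected and that the first result is favourable. Only the correlation of about 0.55 is derived from plan figures, and that also rests on normal scores and on all NDD being Bayley below 85. Two-sided testing is assumed, and the 5% family level is implied, not stated.

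**What to change.** In section 3.1, and in the same words in the separate statistical analysis plan, before unblinding, replace the Bonferroni sentence with:

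> The two co-primary outcomes are tested with a direction-gated step-down rule (a restriction of Holm) at two-sided familywise alpha 0.05: the smaller p-value is compared with 0.025; if it is significant in favour of the intervention, the other is compared with 0.05; otherwise the other is compared with 0.025. The blinded statisticians report the result under both possible codings of the groups.

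The rule should not be called simply Holm, because two independent analysts might then program the ordinary procedure. Keep the power figures based on 0.025 as conservative, and state the downsides in the plan: the error on a null second outcome, the possible mismatch with 97.5% intervals, and the restriction of the two-outcome gain to a favourable first result.

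The cost is a short text in two places, results under two codings, and a minor protocol amendment, since section 2.9 records Steering Committee approval of the protocol. No additional data are needed.

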3.2 Blinding of statisticians

All data managers, statisticians, and those drawing conclusions will be blinded to group allocation. Two blinded statisticians connected to The Copenhagen Trial Unit, will independently perform all statistical analyses and the two statistical reports will be published as supplemental material.

3.3 Publication plan

Once all data from follow-up assessments has been analysed, the results will be published in a peer-reviewed international journal. Members of the steering group will be offered authorship. Furthermore, one investigator per participating NICU can obtain co-authorship. All authors must fulfil the Vancouver Criteria. The blinded assessor completing the data entries will obtain non-byline co-authorship (51). Ancillary studies with results potentially affecting the main study or compromise its publication, shall not be published before the main results of the follow-up study have been published, as decided by the trial steering committee.

Appendix A: Prioritisation of data for the co-primary outcome moderate-or-severe NDD

NDD = moderate-or-severe neurodevelopmental disability = positive findings for at least one of the four components or NDD based on an informal blinded assessment of all available information

No NDD = no moderate-or-severe neurodevelopmental disability = no positive findings in any of the four components and no NDD based on an informal blinded assessment of all available information

Unclassifiable = if one or more components are unknown and none are positive and there is no informal assessment.

Moderate-or-severe neurodevelopmental disability defined as:

Diagnosis of motor impairment: cerebral palsy with functional impairment corresponding to a GMFCS ≥ 2 , but it is not necessary that a GMFCS grading is available from the health care records)

Diagnosis of visual impairment: defined as moderate reduced vision or worse (blind in one eye with good vision in the contralateral eye or blind or can only perceive light or light reflecting objects).

Diagnosis of hearing impairment: defined as hearing loss corrected with aids or some hearing loss not corrected by aids or no useful hearing even with aids.

Cognitive impairment:

- Bayley-III/IV cognitive score < 85 (1st priority)
- Any developmental assessment $< -2SD$ (including the PARCA-R) (2nd priority)
- If none of the above are available, blinded assessment of health care records from 12 months of corrected age and onwards concluding that the child has a cognitive impairment equivalent to moderate or-severe neurodevelopmental disability (3rd priority).

Informal assessment of moderate-or-severe NDD

When there are no relevant health care records from corrected age 18-30 months the records will be accessed by a the blinded assessor and all health care records from corrected age 12 months and onwards will be informally assessed to conclude whether or not the child has moderate-or-severe neurodevelopmental disability.

Prioritisation and possible substitution of data will be done centrally.

Appendix B: Classification of NDD based on parental questionnaire (in cases where components of the co-primary outcomes are unknown or if it is not possible for the blinded assessor to assess NDD based on the health care records):

YES to cerebral palsy: A doctor has said the child has cerebral palsy
 The child CANNOT walk independently at two years of age

NO to cerebral palsy: A doctor has said the child has cerebral palsy
 The child CAN walk independently at two years of age

NO to cerebral palsy: A doctor has NOT said the child has cerebral palsy
 The child CANNOT walk independently at two years of age

NO to cerebral palsy: A doctor has NOT said the child has cerebral palsy
 The child CAN walk independently at two years of age

YES to visual impairment: The child is blind in one or two eyes OR has poor vision even with
 glasses

NO to visual impairment: The child has visual problems
 The child wears glasses
 The child has a squint (the eyes look in different directions)

YES to hearing impairment: The child wears aids or cochlear implants

The child will be categorised as no moderate-or-severe NDD if all components are "no".

The child will be categorised as "not able to classify", if one or more components are unknown and none are positive. Thereby all four components of the primary outcome must be "no", to be classified as no moderate-or-severe NDD.

Example:

From health care records: no to cerebral palsy

From parental questionnaire: no vision impairment,

No clinical record or parental information of hearing impairment or standardised developmental assessment or PARCA-R score.

The child will be “not able to classify”

Appendix C: ancillary studies

The SafeBoosC-III two-year follow-up study will provide important data on the long-term consequences of extreme prematurity. Therefore, we are therefore drafting multiple secondary analyses on data from the SafeBoosC-III trial and follow-up study.

Predictive value of neonatal cerebral ultrasound at 36 weeks postmenstrual age in relation to neurodevelopmental impairment at 24 months of corrected age in extremely preterm infants

In the SafeBoosC-III trial, the primary outcome is a composite of death or severe brain injury. One of the co-primary outcomes of the SafeBoosC-III follow-up study is death or moderate-to-severe neurodevelopmental disability at two years of corrected age. For the purpose of this secondary analysis, the correlation between the brain injury diagnoses included in the ‘severe brain injury’ criteria at 36 weeks PMA and the diagnosis of moderate-to-severe neurodevelopmental impairment at two years of age will be investigated. For the brain injuries cerebral haemorrhage grade III or IV, cystic periventricular leukomalacia, cerebellar haemorrhage, post-haemorrhagic ventricular dilatation or cerebral atrophy, each injury will be computed for the proportion of children with 1) CP (GMFCS ≥ 2) a Bayley III/IV cognitive score below 85, and 3) moderate-or-severe neurodevelopmental disability. To describe the correlation between brain injury diagnosed during the neonatal period and the outcomes, risk ratios will be calculated adjusted for gestational age as well as 95% confidence intervals.

Two-year outcomes of extremely preterm infants: mechanically ventilated vs non-ventilated

In neonates with respiratory failure, mechanical ventilation is a life-saving intervention. It is often the sickest neonates that are requiring mechanical ventilation, whom are frequently suffering from circulatory failure as well. The combination of circulatory and respiratory failure, on top of an increased risk of inadvertent hyperventilation due to the mechanical ventilation, puts this group of neonates in increased risk of cerebral hypoxia (49). Thus, we hypothesise that these neonates would have the largest effect of clinical care with access to cerebral NIRS monitoring. In order to test this hypothesis, we plan to conduct a secondary analysis, comparing children in the experimental group that underwent mechanical ventilation, to children in the experimental group that did not undergo mechanical ventilation and children in the control group, in regard to the two co-primary outcomes of the SafeBoosC-III trial follow-up, as well as the interactions with the group allocation. The

hypothesis is that the effect of the SafeBoosC-III intervention would be greater in ventilated compared to non-ventilated infants.

Correlation between Bayley III/IV and PARCA-R

The PARCA-R questionnaire has previously shown a good correlation to Bayley II and Bayley III scores in national studies (36). However, the literature is sparse when investigating the correlation in an international trial setting using results from routine Bayley tests. The SafeBoosC-III follow-up study plans to make PARCA-R available to the parents of all infants included in the SafeBoosC-III trial. Furthermore, at least 36 NICU will use the Bayley III/IV assessment as an outcome measure. We therefore plan to compare and calculate the correlation between Bayley III/IV scores and PARCA-R scores. The Bayley III/IV cognitive score will be used as a gold standard to assess concurrent validity of the NVC of the PARCA-R. The Pearson correlation coefficient (Pearson's r) will be calculated to assess the relationship between the two continuous measures. Two receiver operating characteristic curves (ROC) will be plotted to investigate the diagnostic accuracy of NVC scores to predict Bayley III/IV cognitive scores below 85, which will be defined as moderate-to-severe neurodevelopmental impairment. The accuracy of the NVC in detecting values below 85 and 70 on the Bayley cognitive scale will be computed by the area under curve measurements.

Standardised mean differences of all assessments used in the SafeBoosC-III follow-up

Since the SafeBoosC-III follow-up study utilises many different assessments, a comparison may be complex. The Bayley III/IV measures differently from the Griffiths, however, the standardised mean difference (SMD) allows for outcomes of similar nature but measured on different scales, to be combined. The SMD will express the possible intervention effect relative to the variability between the developmental tests. This is a commonly used method in meta-analyses. The SMD is used interchangeable with the term "effect size", and is furthermore often used in relation to Cohen's d . The standardisation is obtained by dividing the difference in mean outcome between two groups, with the pooled standard deviation of the measurements. We believe this will provide a valuable point estimate of the effect of the intervention. For the purpose of this analysis, all quantitative scores derived from standardised developmental assessments at two years of corrected age, will be pooled for the statistical analyses and test values will be converted to SMD and will thus allow for comparison between the control and experimental group. All analyses will be intention to treat analyses.

References

1. Blencowe, H., S. Cousens, M.Z. Oestergaard, et al., National, regional, and worldwide estimates of preterm birth rates in the year 2010 with time trends since 1990 for selected countries: a systematic analysis and implications, *The Lancet (British edition)*, 2012. **379**(9832): p. 2162-2172.
2. Cheong, J.L.Y., P.J. Anderson, A.C. Burnett, et al., Changing Neurodevelopment at 8 Years in Children Born Extremely Preterm Since the 1990s, *Pediatrics*, 2017. **139**(6).
3. Norman, M., B. Hallberg, T. Abrahamsson, et al., Association Between Year of Birth and 1-Year Survival Among Extremely Preterm Infants in Sweden During 2004-2007 and 2014-2016, *JAMA*, 2019. **321**(12): p. 1188-1199.
4. Stoll, B.J., N.I. Hansen, E.F. Bell, et al., Trends in Care Practices, Morbidity, and Mortality of Extremely Preterm Neonates, 1993-2012, *JAMA*, 2015. **314**(10): p. 1039-51.
5. Costeloe, K.L., E.M. Hennessy, S. Haider, et al., Short term outcomes after extreme preterm birth in England: comparison of two birth cohorts in 1995 and 2006 (the EPICure studies), *BMJ*, 2012. **345**: p. e7976.

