1.2.2 The SafeBoosC III trial

SafeBoosC III is a multi-centre, international, pragmatic phase III clinical trial investigating the effects of treatment guided by cerebral NIRS monitoring in extremely preterm infants (15). The hypothesis is that treatment based on cerebral NIRS monitoring of cerebral oxygenation in extremely preterm infants will result in a reduction of death or severe brain injury at 36 weeks' PMA. Infants randomised to the experimental group are monitored during the first 72 hours of life and receive cardio-respiratory support guided by cerebral NIRS monitoring (11). The NIRS sensor must be placed within six hours from birth. The control group does not receive any cerebral NIRS monitoring and is treated according to local guidelines and clinical practices. The SafeBoosC III trial will randomise 1600 infants, having started in June 2019 with recruitment expected to be completed by the end of 2021. Nearly 90 neonatal intensive care units (NICUs) from Europe, USA, China and India have signed up to take part in the trial (15). As of May 1st 2021, over 1000 infants have been randomised. The trial is registered at clinicaltrials.gov (NCT03770741).

The original sample size of the SafeBoosC III trial is calculated based on the primary outcome, which is a composite of death or severe brain injury at 36 weeks' PMA (16). Severe brain injury is defined as cerebral haemorrhage grade III or IV, cystic periventricular leukomalacia, cerebellar haemorrhage, post-haemorrhagic ventricular dilatation or cerebral atrophy detected on any of the cerebral ultrasound scans that are routinely performed in these infants up until 36 weeks' PMA or discharge to home, whichever comes first.

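### Appendix C's lead ventilation comparison is non-randomised and confounded by severity; only the appended interaction with allocation can test the hypothesis, and the timing of ventilation status is undefined

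*Combined protocol and SAP*

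**What the plan says.** The ventilation item in Appendix C (ancillary studies) states its aim as effect modification: "The hypothesis is that the effect of the SafeBoosC-III intervention would be greater in ventilated compared to non-ventilated infants". To test this, it plans "comparing children in the experimental group that underwent mechanical ventilation, to children in the experimental group that did not undergo mechanical ventilation" and adds the control group as another comparator, without dividing controls by ventilation. The outcomes are given as "in regard to the two co-primary outcomes of the SafeBoosC-III trial follow-up". The sentence ends by adding "as well as the interactions with the group allocation".

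Two other statements bear on the point. The same item explains why these infants were chosen: "It is often the sickest neonates that are requiring mechanical ventilation", frequently with circulatory failure too. Section 1.2.2 says that infants in the experimental arm "receive cardio-respiratory support guided by cerebral NIRS monitoring" over the first 72 hours, and that "The NIRS sensor must be placed within six hours from birth".

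The plan does not say when ventilation status is determined: before randomisation, during the 72 hours, or at any time. It gives no model for the interaction, no proportion ventilated and no outcome risk by ventilation status.

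**The concern.** The hypothesis concerns a difference between two treatment effects, so it needs experimental versus control among ventilated infants, the same among non-ventilated infants, and a comparison of the two. The lead comparison supplies neither effect. Within the experimental arm there is no treatment contrast at all. Against the whole control arm, a sicker subgroup is set beside an unselected group. Neither keeps the balance that randomisation provides.

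At stake is the reading of this ancillary report. A difference caused by severity could be presented as evidence about the intervention, and a real benefit in ventilated infants could be hidden or appear reversed. The interaction does not share that fault. However, it depends on ventilation strata that allocation cannot have altered, and the plan does not secure this.

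**Working it through.** **What the plan gives.** It states no figure for this analysis, so there is none to reproduce. From section 3 come a control-group composite risk of 50%, 800 infants per arm and a target difference of 8 points. Everything else below is assumed, and all of it concerns the composite outcome. The reasoning applies equally to the Bayley mean but is not quantified for it.

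**Step 1: lead contrasts with zero treatment effect.** Let v be the proportion ventilated, and pV and pN the risks in ventilated and non-ventilated infants, the same in both arms. Then:

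- ventilated minus non-ventilated, within the experimental arm = pV − pN
- ventilated experimental minus all controls = pV − [v·pV + (1 − v)·pN] = (1 − v)(pV − pN)

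Assumed ranges: v 50-70%, pV 55-60%, pN 35-40%.

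| v | pV / pN | Overall risk | Within arm | Versus all controls |
|---|---|---|---|---|
| 50% | 60% / 35% | 47.5% | 25 | 0.5 × 25 = 12.5 |
| 60% | 60% / 35% | 50% | 25 | 0.4 × 25 = 10 |
| 70% | 55% / 35% | 49% | 20 | 0.3 × 20 = 6 |
| 70% | 55% / 40% | 50.5% | 15 | 0.3 × 15 = 4.5 |

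Over the assumed ranges the spurious differences are 15-25 points and 4.5-12.5 points. The interaction is (pV − pV) − (pN − pN) = 0 in every row.

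**Step 2: how often this would be declared significant.** Take 800 per arm, v = 70%, risks of 56% and 36% (overall 50%) and a two-sided 5% test.

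- Within arm: SE = √(0.56·0.44/560 + 0.36·0.64/240) = 0.037, so a 20-point gap is significant in about 100% of trials.
- Versus controls: SE = √(0.56·0.44/560 + 0.25/800) = 0.027, so a 6-point gap is significant in about 59%.

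Over a wider range (50-90% ventilated, gaps of 10-30 points, overall risk 50%) the within-arm contrast is significant in 41-100% of trials with no treatment effect.

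**Step 3: the hypothesis is true.** Take v = 60% and risks of 60% and 35%, with an 8-point benefit in ventilated infants only. Ventilated experimental risk is 60 − 8 = 52%. That is 52 − 35 = 17 points worse than non-ventilated experimental infants and 52 − 50 = 2 points worse than controls. Both lead contrasts point the wrong way, whereas the interaction recovers (52 − 60) − (35 − 35) = −8 points.

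**Step 4: ventilation status taken after allocation.** Suppose 70% are ventilated whatever their allocation (risk 55%), a further fraction s is ventilated only if allocated to the experimental arm, and the rest are never ventilated (risk 35%). Allocation has no effect on outcome. With s = 10%:

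- If the additional infants have risk 35%, experimental ventilated risk is (0.70·0.55 + 0.10·0.35)/0.80 = 52.5% against 55% in controls. The non-ventilated risks are equal, so the interaction is −2.5 points.
- If they have risk 55%, control non-ventilated risk is (0.20·0.35 + 0.10·0.55)/0.30 = 41.7% against 35% in the experimental arm. The ventilated risks are equal, so the interaction is 0 − (−6.7) = +6.7 points.

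For s of 2-10% and risks of 35-55% in the additional infants, the spurious interaction runs from about −2.5 to +6.7 points.

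**Step 5: power of the interaction.** Assume 800 per arm, 50% risk in both control strata, an 8-point benefit in ventilated infants and none in the others, and a two-sided 5% test. SE² = (0.50·0.50 + 0.42·0.58)/(800v) + 2·0.25/(800(1 − v)). At v = 70%, SE = 0.0545, 0.08/SE = 1.47 and power is 31%. At 50, 80 and 90% ventilated, power is 36, 25 and 16%.

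**The case against.** The strongest reply is that the plan already contains the right analysis. The sentence goes on to "as well as the interactions with the group allocation", and a ventilation-by-allocation interaction is the correct quantity for the stated hypothesis. It also cannot be computed without ventilation status in controls, so they must be divided at that point. A reader might infer that the analysis as a whole cannot test its hypothesis. The documents do not support that: the failure belongs to the lead comparison. What remains is that the interaction is an addition with no model, no statement that it decides the question, and no rule for the case where it disagrees with the comparison placed before it.

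A reader might also infer that ventilation is a post-randomisation variable here. The plan does not say so; the wording would fit status at baseline or at any later time. What stands is that the time point is undefined, and that section 1.2.2 makes an influence of allocation on later ventilation plausible.

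Finally, this is an ancillary study still being drafted. Section 3.1 rests any superiority claim on the two co-primary outcomes, and section 3.3 holds back ancillary results that could affect the main study until it is published. All of that stands and limits the importance of the point. The sizes above are illustrations, not estimates.

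**Conclusion.** The point holds for the lead comparison and for the undefined timing of ventilation. The three-group contrast is not randomised and carries severity by the plan's own account. Under the assumed inputs it shows 15-25 points (within arm) and 4.5-12.5 points (versus controls) with no treatment effect, beside a target effect of 8 points for the whole trial. The direction follows from the plan's own statement that ventilated infants are often the sickest; the size depends on ventilation and risk figures that the plan does not give.

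The interaction is the only planned element that tests "the effect of the SafeBoosC-III intervention would be greater in ventilated compared to non-ventilated infants". It is unbiased in the illustration when the strata are fixed before allocation can act. It can be off by a few points in either direction if they are not. The co-primary analyses and conclusions are untouched.

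**What to change.** In the ventilation item of Appendix C:

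- Drop the three-group comparison, or label it descriptive and state that it is not evidence about the intervention.
- Name the ventilation-by-allocation interaction, added to the primary model of section 3.1, as the sole test of the hypothesis. Report experimental-versus-control estimates with confidence intervals within each ventilation stratum.
- Define ventilation status at randomisation, before the intervention starts. If only later status is recorded, say so and draw no conclusion about effect modification.
- Acknowledge the low power of the interaction test (16-36% in the illustration), so that a null result is not read as equal effects.

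The cost is a change of wording, fewer infants per contrast and wider intervals. Status at randomisation would also count infants first ventilated later as non-ventilated, which narrows the question somewhat. In return, the strata cannot be changed by allocation.
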